12.6 Sample Size Calculation

The primary purpose of this study is to investigate to study the effect of supervised exercise training on cardiopulmonary function in men receiving the combination of enzalutamide (ENZ) and androgen deprivation therapy (ADT) for treatment of hormone-naïve prostate cancer.

The initial sample size calculations was based on the expected change in VO₂peak based on relevant prior reports or unpublished observations by the study team. Regarding the ENZ + ADT group, Segal et al.⁸⁰ reported that VO₂peak showed a mean decrease of 1.4 mL.kg.⁻¹min⁻¹ in 41 men initiating radiation with or without ADT for prostate cancer. During the same period, structured supervised resistance training completely abrogated the decline in VO₂peak observed in the usual care group. In unpublished data from our group among 50 men following prostatectomy for localized prostate cancer, mean VO₂peak was 29.5 mL.kg.⁻¹min⁻¹ (± 5.0 mL.kg.⁻¹min⁻¹). Following baseline assessments, subjects were randomly allocated to supervised aerobic training (n=25) or usual care (n=25) for 6 months. VO₂peak increased by 2.71 ± 3.5 mL.kg⁻¹.min⁻¹ in the exercise group and 0.6 ± 2.2 mL.kg⁻¹.min⁻¹ in the usual care group, resulting in a between group difference of +1.95 mL.kg⁻¹.min⁻¹ that favored the exercise training group (p=0.024).

Against this background, this protocol adopted the following assumptions: (1) a decline of 2.0 mL.kg⁻¹.min⁻¹ ENZ-ADT group from baseline to 16 weeks, and (2) an increase of 1.0 mL.kg⁻¹.min⁻¹ ENZ-ADT plus exercise training group from baseline to 16 weeks, for a between group delta of 3.0 mL.kg⁻¹.min⁻¹, favoring the ENZ-ADT plus exercise training group. A total of 56 subjects (n=28 / per group) provides 80% power to detect a mean 3.0 mL.kg⁻¹.min⁻¹ between group difference in VO₂peak from baseline to post-intervention, assuming a SD of 3.5 mL.kg⁻¹.min⁻¹ and a two-sided alpha of 0.05. These calculations assume a lost-to-follow-up rate of 15%, thus approximately 23 per group will provide evaluable data at 16 weeks post-randomization.

In November 2016, an interim analysis was performed due to the slow accrual and subjective feedback from subjects and exercise physiologists. That is, subjects in the exercise training group (Arm B) seemed to feel and perform better after the 16-week exercise training program compared with the usual care (Arm A) group at

the same time point. A difference in the point estimates of $\Delta\text{VO}_2\text{peak}$ (week 1 to week 17) between groups was seen in the first 8 subjects who had completed testing for the primary endpoint of $\Delta\text{VO}_2\text{peak}$ at week 17 (N=4 each in the usual care and exercise training groups), suggesting less decline of VO_2peak in Arm B. Based on the interim analysis data, the study statisticians revised the sample size calculation.

We expect to use a one-sided t-test to check whether Arm B has a significant increase in VO_2peak from the baseline compared to Arm A. When each group has 20 evaluable subjects for significance level 0.10, we have 80% power to reject the null hypothesis that the two groups have the same change of VO_2peak given the effect size is 0.68 (the ratio of mean difference over common standard deviation). In case the test result is not significant, we will report the mean reduction descriptively with 95% confidence interval for this pilot study.

In summary, the revised sample size estimate is 40 total evaluable subjects, or 20 subjects in each arm.

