3 STUDY SCHEMA

Primary Objective: To study the effect of supervised exercise training on cardiopulmonary function in men receiving the combination of enzalutamide (ENZ) and androgen deprivation therapy (ADT) for treatment of non-metastatic, hormone-naïve prostate cancer.

Design: Subjects with histologically-confirmed, progressive, non-metastatic, hormone-naïve prostate cancer, with a PSA ≥ 0.01 ng/ml, scheduled to be treated with ADT for ≥ 8 months, will be randomly allocated to one of two following arms:

- A. Enzalutamide (ENZ) with androgen deprivation therapy (ADT) (n=20), or
- B. Enzalutamide (ENZ) with androgen deprivation therapy (ADT) plus supervised exercise training (n=20)

*The **Lead-In Period** will consist of 4 weeks of either usual care or combined aerobic and resistance exercise training prior to starting ENZ – ADT. Upon initiation of ENZ – ADT, subjects on Arm B will continue the exercise training program for 12 additional weeks. Hence, **Treatment Period 1** is 16 weeks in total.

†Baseline exercise testing will be done prior to randomization, but after confirmation of eligibility.

[figure not shown]

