6 INVESTIGATIONAL PLAN

6.1 Study Design

This is a two-arm, non-blinded randomized (1:1) phase II trial to determine the efficacy on aerobic capacity of the combination of enzalutamide (ENZ) with androgen deprivation therapy (ADT) compared to the same regimen plus supervised exercise training (ENZ-ADT plus exercise training) in men with hormone-naïve prostate cancer. This study will be conducted at 2 centers: Duke Cancer Institute (DCI) and Memorial Sloan-Kettering Cancer Center (MSKCC). A total of 40 subjects will be enrolled. Subjects will be treated with enzalutamide plus ADT for 32 weeks. If randomized to the exercise arm, subjects will undergo supervised exercise training for 16 weeks.

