6.4 Definition of Evaluable Subjects

For the primary analysis of $\Delta V_{O_2\text{peak}}$, patients with measurements at baseline are evaluable.

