9.11.3 Replacement of Early Withdrawal(s)

Subjects who withdraw prior to completing the baseline assessment for the primary endpoint will be replaced. See also Sections 9.1 and 9.2 for eligibility criteria, as well as 12.1 and 12.4.3 for analysis related to withdrawals.

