12.1 Analysis Sets

The intent-to-treat (ITT) population will consist of all randomized patients. The modified intent-to-treat (ITT) population will consist of all randomized patients who have both a baseline and week 17 evaluation. In the ITT analyses and the modified ITT analyses patients will be analyzed according to the study arm to which they were randomized. The modified ITT population will be the primary analysis population.

The per-protocol population will consist of all randomized patients with both baseline and week 17 measurements for the primary endpoint and prior to any analysis: have been deemed compliant and properly evaluated for efficacy per investigator, satisfied all inclusion and exclusion criteria, and correctly assigned treatment.

The safety population will be all patients with at least one safety evaluation.

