12.4.3 Handling of missing values, censoring, and discontinuations

The primary analysis from baseline to week 17 will include only complete cases.

Patients without VO_2peak measured at week 17 who have one or more measurements during the period from week 17 to the end of week 36 will have their week 17 measurement estimated by interpolation from the end of week 4 to the closest measurement following week 17. A sensitivity analysis will be done including these patients with complete cases.

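### The revised 80% power needs 40 men with week 17 data, but only 40 are enrolled, no loss is allowed for, and Section 6.4 counts men as evaluable on a baseline test alone

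*Combined protocol and SAP*

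**What the plan says.** Section 12.6 bases the revised design on analysable men: "When each group has 20 evaluable subjects for significance level 0.10, we have 80% power", for a one-sided t-test and an effect size of 0.68. It sums up: "In summary, the revised sample size estimate is 40 total evaluable subjects, or 20 subjects in each arm".

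Section 6.1 states "A total of 40 subjects will be enrolled", and the schema in Section 3 gives 20 per arm.

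The primary analysis needs both tests. Section 12.1 makes the modified ITT population primary and says it "will consist of all randomized patients who have both a baseline and week 17 evaluation". Section 12.4.2 specifies complete cases, and Section 12.4.3 repeats: "The primary analysis from baseline to week 17 will include only complete cases".

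Section 6.4 says otherwise: for the primary analysis of change in VO2peak, "patients with measurements at baseline are evaluable".

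There are two replacement rules. Section 6.1.4 replaces men who do not receive their assigned treatment and leaves them out of the sample size count. Section 9.11.3 says: "Subjects who withdraw prior to completing the baseline assessment for the primary endpoint will be replaced".

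**The concern.** The number required for analysis and the number to be enrolled are the same, so there is no margin for loss. The initial calculation in Section 12.6 kept the two apart: 28 per group enrolled, 15% lost, about 23 per group with data at 16 weeks. The revision kept the term evaluable but states no loss allowance.

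Section 6.4 hides the gap. Baseline CPET comes before randomisation, so under that definition essentially every randomised man is evaluable on entry. The target of 40 could then be declared met while the t-test has fewer men. A non-significant result would be judged against a stated 80% power that the trial did not have.

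**Working it through.** **Inputs.** From Section 12.6: one-sided alpha 0.10, effect size d = 0.68, 20 evaluable per arm, 80% power. From Sections 3 and 6.1: 40 enrolled, 20 per arm. The only loss rate in the documents is the 15% in the initial calculation. For the revised plan, every loss rate below is an assumption, shown as a range.

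**Formula.** Two-sample t-test: power = P(T > t₀.₉₀,df), where T is noncentral t with df = n₁ + n₂ − 2 and noncentrality d / √(1/n₁ + 1/n₂).

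**Reproducing the plan's figure.** With 20 per arm, df = 38, the critical value is 1.304 and the noncentrality is 0.68 × √10 = 2.150. Power is 80.1%, so the stated 80% is correct for 20 analysed men per arm.

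**Power after loss.** Loss here is net of any replacement.

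| Men analysed per arm | Net loss from 40 | Power at d = 0.68 | d giving 80% power |
|---|---|---|---|
| 20 and 20 | none | 80.1% | 0.68 |
| 20 and 19 | one man | 79.3% | – |
| 19 and 19 | 5% | 78.5% | 0.70 |
| 18 and 18 | 10% | 76.8% | 0.72 |
| 17 and 17 | 15% | 75.0% | 0.74 |
| 16 and 16 | 20% | 73.1% | 0.76 |

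If each man is instead lost at random with the given probability, average power is 78.5%, 76.7%, 74.8% and 72.8% for 5%, 10%, 15% and 20% loss. The conclusion does not change.

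**Enrolment needed to keep 20 analysed per arm.** 20/0.95 = 21.1, so 22 per arm (44 in total); 20/0.90 = 22.2, so 23 (46); 20/0.85 = 23.5, so 24 (48).

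**The initial design, for comparison.** 28 × 0.85 = 23.8, which the plan gives as about 23. At d = 3.0/3.5 = 0.857 and two-sided 0.05, 23 per arm gives 81.1%. That version did reach its stated power after loss.

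**Does another rule fill the gap?**

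- Section 6.1.4 covers men who do not receive the assigned treatment.
- Section 9.11.3 covers withdrawal before the baseline assessment.
- A man who begins treatment and then has no week 17 CPET falls under neither, on the natural reading.
- The interpolation in Section 12.4.3 is a sensitivity analysis. It also needs a measurement after week 17, and the schedule has no CPET after Day 113.
- The last-observation-carried-forward analysis in Sections 5 and 12.5 could use the Day 29 CPET, but it too is a sensitivity analysis. Neither adds men to the primary test.

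**The case against.** The strongest reply is that nothing is miscalculated. Section 12.6 makes its power conditional on 20 evaluable men per arm, and on that condition it is right. This stands: the fault is a missing loss allowance and a conflicting definition, not the 80% itself.

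The shortfall is also small beside the uncertainty in the effect size. At the initially assumed 0.857, 17 per arm would give 88% power; at 0.60, even 20 per arm gives only 72%. If the earlier SD of 3.5 still applied, moving from 0.68 to 0.74 is about 0.2 mL/kg/min. This stands too, and it limits the weight of the point.

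Third, if the test is not significant, Section 12.6 plans a descriptive report with a 95% confidence interval, which reflects the number actually analysed. That reduces the risk of misreading but does not correct the stated power.

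Fourth, replaced men are not counted, so more than 40 could be randomised, and failure to receive the assigned treatment is undefined for a 16-week programme. A broad reading could cover some later loss, but the text does not say so.

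Finally, nothing shows that accrual would be closed on baseline-only counts. Sections 12.1, 12.4.2 and 12.4.3 agree with each other, and the initial calculation in Section 12.6 ties evaluable data to 16 weeks. The conflict with Section 6.4 still has to be removed.

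**Conclusion.** The concern holds. The revised plan reaches 80% power only if all 40 counted men have VO2peak at baseline and week 17; one net loss takes it to 79.3%. Over assumed net losses of 5% to 20%, power is 78.5% to 73.1%. The 75.0% at 15% loss assumes that the initial rate carries over with no replacement. All these figures take d = 0.68 as given.

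The contradiction between Section 6.4 and Sections 12.1 and 12.4 does not depend on any loss rate. The point should be fixed; its numerical effect is modest.

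**What to change.** 1. **Section 12.6.** State the assumed loss, the expected number of completers and the power that follows. For example: *Enrolment is 40. If 15% lack a week 17 CPET, about 34 men (17 per arm) enter the primary analysis, giving about 75% power at effect size 0.68, or 80% at 0.74, with one-sided alpha 0.10.* Here 40 × 0.85 = 34. The 15% is only illustrative; the sponsor should insert the rate it expects.
2. **Section 6.4.** Replace the definition with: *A man is evaluable for the primary analysis of change in VO2peak if it was measured at both baseline and week 17.*
3. **Section 6.1.4 (clarification).** Say that a replaced man who was randomised stays in the ITT population in his assigned arm, as Section 12.1 already implies, and that his Day 113 CPET is sought. Any such man with both tests enters the modified ITT set, so the completer count in Section 12.6 should say whether it includes these men.

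The cost is wording and a slightly less favourable power statement. If the sponsor prefers to keep 80%, enrolment becomes 44, 46 or 48 for 5%, 10% or 15% net loss, which is hard given the slow accrual noted in Section 12.6.

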13 ADMINISTRATIVE AND ETHICAL CONSIDERATIONS

13.1 Regulatory and Ethical Compliance

This protocol was designed and will be conducted and reported in accordance with the International Conference on Harmonization (ICH) Harmonized Tripartite Guidelines for Good Clinical Practice, the Declaration of Helsinki, and applicable federal, state, and local regulations.

13.2 DUHS Institutional Review Board and DCI Cancer Protocol Committee

The protocol, informed consent form, advertising material, and additional protocol-related documents must be submitted to the DUHS Institutional Review Board (IRB) and DCI Cancer Protocol Committee (CPC) for review. The study may be initiated only after the Principal Investigator has received written and dated approval from the CPC and IRB.

The Principal Investigator must submit and obtain approval from the IRB for all subsequent protocol amendments and changes to the informed consent form. The CPC should be informed about any protocol amendments that potentially affect research design or data analysis (i.e. amendments affecting subject population, inclusion/exclusion criteria, agent administration, statistical analysis, etc.).

The Principal Investigator must obtain protocol re-approval from the IRB within 1 year of the most recent IRB approval. The Principal Investigator must also obtain protocol re-approval from the CPC within 1 year of the most recent IRB approval, for as long as the protocol remains open to subject enrollment.

13.3 Informed Consent

The informed consent form must be written in a manner that is understandable to the subject population. Prior to its use, the informed consent form must be approved by the IRB.

The Principal Investigator or authorized key personnel will discuss with the potential subject the purpose of the research, methods, potential risks and benefits, subject concerns, and other study-related matters. This discussion will occur in a location that ensures subject privacy and in a manner that minimizes the possibility of coercion. Appropriate accommodations will be made available for potential subjects who cannot read or understand English or are visually impaired. Potential subjects will have the opportunity to contact the Principal investigator or authorized key personnel with questions, and will be given as much time as needed to make an informed decision about participation in the study.

Before conducting any study-specific procedures, the Principal Investigator must obtain written informed consent from the subject or a legally acceptable representative. The original informed consent form will be stored with the subject's study records, and a copy of the informed consent form will be provided to the subject.

13.4 Privacy, Confidentiality, and Data Storage

The Principal Investigator will ensure that subject privacy and confidentiality of the subject's data will be maintained. Research Data Security Plans (RDSPs) will be approved by the appropriate Duke clinical research unit for the Duke site.

To protect privacy, every reasonable effort will be made to prevent undue access to subjects during the course of the study. Prospective participants will be consented in an exam room where it is just the research staff, the patient and his family, if desired. For all future visits, interactions with research staff (study doctor and study coordinators) regarding research activities will take place in a private exam room. All research related

interactions with the participant will be conducted by qualified research staff who are directly involved in the conduct of the research study.

To protect confidentiality, subject files in paper format will be stored in secure cabinets under lock and key accessible only by the research staff. Electronic records of subject data will be maintained using a dedicated database which is housed in an encrypted and password-protected DCI file server. Access to electronic databases will be limited to delegated personnel. The security and viability of the IT infrastructure will be managed by the DCI and/or Duke Medicine.

Upon completion of the study, research records will be archived and handled per DUHS HRPP policy. Subject names or identifiers will not be used in reports, presentations at scientific meetings, or publications in scientific journals.

13.5 Data and Safety Monitoring

Data and Safety Monitoring will be performed in accordance with the DCI Data and Safety Monitoring Plan. For a more detailed description of the DSMP for this protocol, refer to Section 11 (Sections 11.6 and 11.7 in particular) and Section 12.

13.6 Protocol Amendments

All protocol amendments must be initiated by the Principal Investigator and approved by the IRB prior to implementation. IRB approval is not required for protocol changes that occur to protect the safety of a subject from an immediate hazard. However, the Principal Investigator must inform the IRB and all other applicable regulatory agencies of such action immediately.

Though not yet required, the CPC should be informed about any protocol amendments that potentially affect research design or data analysis (i.e. amendments affecting subject population, inclusion/exclusion criteria, agent administration, etc.).

13.7 Records Retention

The Principal Investigator at each site will maintain study-related records at least six years after study completion.

13.8 Conflict of Interest

The Principal Investigator and Sub-Investigators must comply with applicable federal, state, and local regulations regarding reporting and disclosure of conflict of interest. Conflicts of interest may arise from situations in which financial or other personal considerations have the potential to compromise or bias professional judgment and objectivity. Conflicts of interest include but are not limited to royalty or consulting fees, speaking honoraria, advisory board appointments, publicly-traded or privately-held equities, stock options, intellectual property, and gifts.

The Duke University School of Medicine's Research Integrity Office (RIO) reviews and manages research-related conflicts of interest. The Principal Investigator and Sub-Investigators must report conflicts of interest annually and within 10 days of a change in status, and when applicable, must have a documented management plan that is developed in conjunction with the Duke RIO and approved by the IRB/IEC.

14 APPENDICES

Appendix A PERFORMANCE STATUS CRITERIA

ECOG Performance Status Scale		Karnofsky Performance Scale	
Grade	Descriptions	Percent	Description
0	Normal activity. Fully active, able to carry on all pre-disease performance without restriction.	100	Normal, no complaints, no evidence of disease.
		90	Able to carry on normal activity; minor signs or symptoms of disease.
1	Symptoms, but ambulatory. Restricted in physically strenuous activity, but ambulatory and able to carry out work of a light or sedentary nature (e.g., light housework, office work).	80	Normal activity with effort; some signs or symptoms of disease.
		70	Cares for self, unable to carry on normal activity or to do active work.
2	In bed <50% of the time. Ambulatory and capable of all self-care, but unable to carry out any work activities. Up and about more than 50% of waking hours.	60	Requires occasional assistance, but is able to care for most of his/her needs.
		50	Requires considerable assistance and frequent medical care.
3	In bed >50% of the time. Capable of only limited self-care, confined to bed or chair more than 50% of waking hours.	40	Disabled, requires special care and assistance.
		30	Severely disabled, hospitalization indicated. Death not imminent.
4	100% bedridden. Completely disabled. Cannot carry on any self-care. Totally confined to bed or chair.	20	Very sick, hospitalization indicated. Death not imminent.
		10	Moribund, fatal processes progressing rapidly.
5	Dead.	0	Dead.

Appendix B and C FACT-P and FACIT FATIGUE SCALE (VERSION 4)

Below is a list of statements that other people with your illness have said are important.
Please circle or mark one number per line to indicate your response as it applies to the past 7 days.

PHYSICAL WELL-BEING

		Not at all	A little bit	Some-what	Quite a bit	Very much
GP1	I have a lack of energy.....	0	1	2	3	4
GP2	I have nausea	0	1	2	3	4
GP3	Because of my physical condition, I have trouble meeting the needs of my family	0	1	2	3	4
GP4	I have pain	0	1	2	3	4
GP5	I am bothered by side effects of treatment	0	1	2	3	4
GP6	I feel ill	0	1	2	3	4
GP7	I am forced to spend time in bed	0	1	2	3	4

SOCIAL/FAMILY WELL-BEING

		Not at all	A little bit	Some-what	Quite a bit	Very much
GS1	I feel close to my friends	0	1	2	3	4
GS2	I get emotional support from my family	0	1	2	3	4
GS3	I get support from my friends.....	0	1	2	3	4
GS4	My family has accepted my illness	0	1	2	3	4
GS5	I am satisfied with family communication about my illness.....	0	1	2	3	4
GS6	I feel close to my partner (or the person who is my main support).....	0	1	2	3	4
Q1	Regardless of your current level of sexual activity, please answer the following question. If you prefer not to answer it, please mark this box  and go to the next section.					
GS7	I am satisfied with my sex life.....	0	1	2	3	4

Please circle or mark one number per line to indicate your response as it applies to the past 7 days.

EMOTIONAL WELL-BEING

GE1
GE2
GE3
GE4
GE5
GE6

		Not at all	A little bit	Some- what	Quite a bit	Very much
GE1	I feel sad.....	0	1	2	3	4
GE2	I am satisfied with how I am coping with my illness	0	1	2	3	4
GE3	I am losing hope in the fight against my illness	0	1	2	3	4
GE4	I feel nervous	0	1	2	3	4
GE5	I worry about dying	0	1	2	3	4
GE6	I worry that my condition will get worse	0	1	2	3	4

FUNCTIONAL WELL-BEING

GF1
GF2
GF3
GF4
GF5
GF6
GF7

		Not at all	A little bit	Some- what	Quite a bit	Very much
GF1	I am able to work (include work at home).....	0	1	2	3	4
GF2	My work (include work at home) is fulfilling	0	1	2	3	4
GF3	I am able to enjoy life	0	1	2	3	4
GF4	I have accepted my illness	0	1	2	3	4
GF5	I am sleeping well.....	0	1	2	3	4
GF6	I am enjoying the things I usually do for fun.....	0	1	2	3	4
GF7	I am content with the quality of my life right now	0	1	2	3	4

Please circle or mark one number per line to indicate your response as it applies to the past 7 days.

	GENERAL ADDITIONAL CONCERNS	Not at all	A little bit	Some-what	Quite a bit	Very much
C2	I am losing weight	0	1	2	3	4
C6	I have a good appetite	0	1	2	3	4
P1	I have aches and pains that bother me	0	1	2	3	4
P2	I have certain parts of my body where I experience pain...	0	1	2	3	4
P3	My pain keeps me from doing things I want to do	0	1	2	3	4
P4	I am satisfied with my present comfort level	0	1	2	3	4
P5	I am able to feel like a man.....	0	1	2	3	4
P6	I have trouble moving my bowels	0	1	2	3	4
P7	I have difficulty urinating	0	1	2	3	4
BL2	I urinate more frequently than usual.....	0	1	2	3	4
P8	My problems with urinating limit my activities	0	1	2	3	4
BL5	I am able to have and maintain an erection	0	1	2	3	4

Please circle or mark one number per line to indicate your response as it applies to the past 7 days.

	FATIGUE ADDITIONAL CONCERNS	Not at all	A little bit	Some- what	Quite a bit	Very much
HI7	I feel fatigued.....	0	1	2	3	4
HI12	I feel weak all over	0	1	2	3	4
An1	I feel listless ("washed out").....	0	1	2	3	4
An2	I feel tired.....	0	1	2	3	4
An3	I have trouble starting things because I am tired	0	1	2	3	4
An4	I have trouble finishing things because I am tired.....	0	1	2	3	4
An5	I have energy	0	1	2	3	4
An7	I am able to do my usual activities	0	1	2	3	4
An8	I need to sleep during the day	0	1	2	3	4
An12	I am too tired to eat.....	0	1	2	3	4
An14	I need help doing my usual activities	0	1	2	3	4
An15	I am frustrated by being too tired to do the things I want to do	0	1	2	3	4
An16	I have to limit my social activity because I am tired	0	1	2	3	4

